10.3.1. Primary Outcomes

➤ Implementation effectiveness outcome

For the implementation effectiveness primary outcome (*number of guideline-appropriate CRC screening recommendations provided*), a study specific data collection instrument will be used and integrated into Clinical Information Systems (CIS) used in general practice. CISs are used by general practices to facilitate care at an individual patient level. Medical records are stored within the CIS and used by GPs to store information during consultations, such as patient bowel cancer screening history. The National Cancer Screening Register (NCSR) integrates with CIS to allow health providers access to patients' NBCSP participation history from within their CIS.

Medical Director is a CIS used widely across Australia and is already integrated into practices across NSW and WA. Medical Director will enter into an agreement with the University of Sydney under a "Education Support – Master Services Agreement". The agreement will include the development of an electronic prompt which will act as a study specific data collection instrument. Medical Director obtains consent from general practices where their software has been installed to participate in research project. Data will be extracted from the general practice CIS via Medical Director and is de-identified, and no identifiable data leaves the CIS. Medical Director data are managed in accordance with relevant privacy and health records legislation.

➤ *Clinical effectiveness outcome*

For the clinical effectiveness primary outcome of the *number of guideline-appropriate CRC screening tests completed by patients*, de-identified, aggregate patient data will be extracted from CIS. These data will be obtained from the PHN (Health Analytics Software).

PHNs collect data from general practice electronic medical records stored within their CIS through Health Analytics Software tools. The tools used render the data drawn from practice databases unidentifiable, enabling it to be disclosed for research purposes under the Privacy Act 1988 (Privacy Act). PHNs facilitate the licensing of Health Analytics Software to support the extraction, analysis and management of general practice data in the form of population health reports, including bowel cancer screening participation.

Data collection is facilitated by established Data Sharing Agreements between the PHN and general practices within their regions. The Agreement permits the extraction, sharing and use of de-identified practice data to the PHN to support the provision of health services and to improve health policies. The de-identified data may be disclosed to third parties to develop health prevention strategies or support research. PHNs are governed by the PHNs Cooperative's National Data Governance Committee and the PHNs National Data Governance Framework (28). The PHN has ownership and legal accountability of the management and use of the extracted and shared de-identified data through legislative and policy obligations. The software providers are governed by an organisational Privacy Policy related to the collection and storage of de-identified health data (28–30). The software providers encrypt de-identified data for transmission over secure channels.

General practices are required to display privacy notices within the practice of which Health Analytics Software they are using with disclosure that the information is secure and cannot identify patients. Patients may request that the general practice not collect or share their data. It is the responsibility of the general practices to obtain and manage patients' consent for their de-identified data to be shared beyond the practice CIS.

10.3.2. Secondary Outcomes

For the secondary outcomes, questionnaires have been adapted from previous Australian studies to determine these outcomes (18,31). The questionnaires will be conducted at three time points:

1. Pre: on recruitment to determine baseline awareness and existing activities
2. Mid: before the intervention is delivered to determine the potential impact of non-study activities to build awareness and/or encourage CRC screening (if they have been in field)
3. Post: on completion to determine intervention outcomes

A practice 'readiness for change' questionnaire was developed based on the Cancer Institute NSW 'Primary Care Toolkit: readiness checklist' (20). In addition to assessing 'readiness for change' the survey will determine General Practice characteristics and staff demographics. As these items are directly relevant to the trial, all practices in both the intervention and control group are required to complete the questionnaire, pre- and post- intervention delivery by a general practice representative. This questionnaire will take up to 10 minutes to complete and is available in the Appendix 4E and 4F.

Participating clinicians (GPs, nurses) and general practice staff will be invited to complete the 'Awareness and current knowledge of the NBCSP' questionnaire at baseline and trial close, adapted from the South Eastern Melbourne Primary Health Network Evaluation Report 2019 (31). The questionnaire has been adapted to include the validated Influences on Patient Safety Behaviours Questionnaire (IPSBQ) (32). The questionnaire will take up to 20 minutes to complete and is provided in full in Appendix 4A and 4B but will be available via a REDcap link.

Participating clinicians (GPs, nurses) and general practice staff in intervention practices will be invited to complete the implementation outcomes survey. This questionnaire is adapted from the validated Acceptability of Intervention Measure (AIM) scale and will assess the perceived acceptability,

appropriateness and feasibility of intervention by participants (33). The questionnaire will be available via a REDCap link at mid-trial and post-trial and will take up to 10 minutes to complete (see Appendix 4C and 4D).

The surveys and questionnaires used in this trial have been previously used and validated and will be used as published. The CTC will invite general practice participants to participate in the questionnaires at the relevant time points via email that contains a REDCap link (see Appendix 1C). The REDCap link will direct participants to a landing page containing the Participant Information Statement and questionnaire.

10.4. Statistical analysis and data analysis

Descriptive statistics will be used to summarise the general practice characteristics for each trial arm and the outcome results.

Intention-to-treat analysis will be used, where all general practices allocated to the trial group will be included and analysed in the group that they were assigned. Both the primary and secondary outcomes will be compared between the intervention and control groups using poisson or negative binomial regression and generalised linear modelling with an identity link function and binomial family to estimate the odds ratio and difference in proportions respectively. The regression models will use generalised estimating equations with robust standard errors to allow for clustering by general practice and will adjust for the randomisation stratification factors (e.g., practice size, state, rurality, socioeconomic indexes for areas (SEIFA) (34)). Both the relative and absolute measures of the estimated intervention effect will be reported with their respective 95% confidence intervals, and a p values calculated from the logistic regression.

The intra-practice correlation, which quantifies the proportion of the total variation in the outcome attributable to between-cluster variation in the outcome will also be estimated using mixed effects modelling and reported with 95% confidence intervals.

Results from the IPSBQ will be analysed using descriptive statistics and multivariate analysis of variance (MANOVA) to assess difference in perceived barriers pre- and post-intervention implementation. Mediation analysis will be performed to assess the degree to which changes in specific barriers influence changes in behaviour (i.e. mechanisms of action).

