10.1.2. Population & sample size

An indicative sample size has been calculated based on documented approximate rules for pilot trials (24). For a main trial designed with 90% power and two-sided 5% significance, pilot trial sample sizes with 50-75 practices per arm for standardised effect sizes ranging from extra small (≤ 0.1) to large (0.8) are recommended (24). We aim to recruit up to 50 general practices per arm with at least two GPs per practice, in line with previous studies despite the sample size calculated based on patient screening behaviour change (25,26). A pilot with up to 100 general practices will yield sufficient information to assess the effectiveness of the intervention.

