10.4.1. Guideline-appropriate screening

Guideline-appropriate screening in Australia is determined based on a clinicians' judgement of a patient's risk of CRC and recommendations in the 2017 Guidelines (3). In this study, patients aged 50-74 years will be classified as either guideline-appropriate screeners (those who undergo screening appropriate for their risk level as directed by their GP) or non-guideline-appropriate screeners (encompassing both under-screeners and over-screeners). For a detailed description of the criteria for guideline-appropriate, under- and over- screening (see Table 4). Contingency tables will be generated to represent the proportion of guideline-appropriate screeners and non-guideline-appropriate screeners in each trial arm, risk category, age group and sex.

For the primary clinical effectiveness outcome (*number of guideline-appropriate CRC screening tests completed by patients*), an incremental approach will be used to test the effect of the intervention. The first model (unadjusted model) will use the trial group as the sole fixed predictor. The second model (adjusted model) will add guideline risk category, gender, age, and socioeconomic status of the practice (based on SEIFA (34)) to the unadjusted model. The final model (effect modification model) will look at the interaction between treatment group and risk category to test whether the effect of the intervention was modified by risk category.

If the final model demonstrates significant effect modification, simple post hoc analyses will be performed at each risk level. Comparisons involving categorical predictors with more than two levels

will be corrected using the Westfall method, a step-down form of error correction that offers similar protection against type I error as traditional single-step methods such as the Bonferroni procedure but is less conservative and, therefore, less likely to overinflate p values and conceal genuine effects (35).

Table 4 Guideline-appropriate screening categorisation (3)

Risk category	Not guideline-appropriate/under screening	Guideline-appropriate screening	Not guideline-appropriate

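### Section 10.4 spreads one comparison over three models, mislabels the odds ratio, and takes the risk difference from an identity-link model that may not fit with patient-level covariates

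*Protocol*

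**What the plan says.** Section 10.4 applies the same models to the primary and secondary outcomes. One is a count regression, either Poisson or negative binomial. The other is given as "generalised linear modelling with an identity link function and binomial family to estimate the odds ratio and difference in proportions respectively". Read with its closing word, that sentence assigns the odds ratio to the count regression and the difference in proportions to the identity-link binomial model.

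The models "will use generalised estimating equations with robust standard errors to allow for clustering by general practice" and are adjusted for practice size, state, rurality and SEIFA. Relative and absolute effects are both promised with 95% confidence intervals, together with "a p values calculated from the logistic regression". No logistic model has been named up to that point.

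For the clinical co-primary outcome, section 10.4.1 builds up in steps. An unadjusted model contains trial group alone. Then: "The second model (adjusted model) will add guideline risk category, gender, age, and socioeconomic status of the practice". A last model adds the interaction of trial group with risk category. Section 10.3.1 says of the data for this outcome that "de-identified, aggregate patient data will be extracted from CIS".

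**The concern.** There are two problems in one sentence.

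The first is a plain error. A Poisson or negative binomial model with its usual log link estimates a rate ratio, or a risk ratio if it is fitted to binary data. It does not estimate an odds ratio. The p value is then attached to a third model, so the relative effect, the absolute effect and the test need not agree or share an adjustment set.

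The second is a fragile choice. An identity link does not hold fitted probabilities between 0 and 1, and it forces covariate effects to add on the probability scale. With several patient-level covariates, one of them a three-level risk category that may have sparse levels, fitting can break down. If it does, the covariates or the model would have to be chosen after the data are seen. Section 15 sends the results to a predictive model for effectiveness and cost-effectiveness work. An absolute effect is plausibly what that model needs, though the protocol does not say so.

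**Working it through.** There is no stated figure to reproduce. The labelling can be checked by arithmetic and the fitting by simulation.

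**Inputs from the protocol.** Up to 50 practices per arm (section 10.1.2), so 100 clusters; binomial family, identity link, GEE with robust standard errors (10.4); practice-level covariates (10.4); risk category in three levels, gender, age and SEIFA (10.4.1 and Table 4).

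**Assumptions, not in the protocol.** Control-arm proportion 2% to 55%; intervention odds ratio 1.3; between-practice SD 0.4 on the logit scale; data generated from a logistic model; 60 patients per practice. The odds ratio in the rarer risk categories, relative to the lowest-risk one, was set at 0.3, 1 or 3.

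**Step 1: the label.** With odds ratio 1.3 and a control proportion of 40%, the intervention proportion is 1.3 × 0.40 / (0.60 + 1.3 × 0.40) = 0.52 / 1.12 = 0.464. The risk ratio is 0.464 / 0.40 = 1.16. At 5% it is 0.065 / 1.015 = 0.0640, and the risk ratio is 1.28. The two measures are close only when the outcome is rare.

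**Step 2: why the identity link can break.** Take a rare risk category with odds ratio 0.3.
- At a base of 5%, its proportion is 0.3 × 0.05 / (0.95 + 0.015) = 0.0155. Any combination of other covariate effects that subtracts more than 1.6 percentage points gives a negative fitted probability.
- At a base of 40%, its proportion is 0.12 / 0.72 = 0.167, which leaves far more room.

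**Step 3: patient-level covariates.** Exchangeable GEE, 30 datasets per cell. Failure means no convergence or non-finite estimates.

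| Control proportion | Identity, no risk effect | Identity, OR 0.3 | Identity, OR 3 | Logistic, worst of the three |
|---|---|---|---|---|
| 2% | 73% | 97% | 40% | 43% |
| 5% | 43% | 100% | 17% | 10% |
| 10% | 13% | 100% | 3% | 0% |
| 20% | 0% | 97% | 0% | 3% |
| 40% | 0% | 23% | 10% | 0% |
| 55% | 0% | 0% | 27% | 0% |

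Monte Carlo error is large. For 43% it is √(0.43 × 0.57 / 30) = 0.09, or 9 percentage points.

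A second run used working independence, an assumed 95/4/1% risk mix and 60 datasets per cell, and counted out-of-range fits as failures:
- no risk effect: 25% at 5%, 7% at 10%, 0% at 40%;
- odds ratio 0.3: 98% at 5%, 97% at 10%, 87% at 20%, 30% at 40%;
- odds ratio 3: 0% to 5%;
- logistic model: no failures.

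A further 40 datasets per cell with the same mix gave 25% at 5% with no risk effect, 93% to 98% at 5% to 10% with odds ratio 0.3, and 0% for the logistic model.

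**Step 4: practice-level covariates only.** One aggregate row per practice, 100 or 300 patients each, 300 datasets per cell, modest covariate effects (log odds 0.1 for state, 0.1 per SD of size, −0.15 for rurality, 0.08 per SEIFA step). The identity-link model failed in 0% to 1% of datasets at every proportion from 2% to 55%. The mean absolute gap from the standardised logistic difference was at most 0.0014.

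**Step 5: does the alternative recover the effect?** With no risk-category effect, the standardised logistic difference averaged 0.0467 against a simulated truth of 0.0469 at 20%, and 0.0605 against 0.0618 at 40%.

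**The case against.** The strongest reply is that this is a preference between accepted methods. Binomial identity-link regression with GEE is a recognised estimator of a risk difference. The protocol nowhere says that the proportions are low. Table 4 classifies patients by looking back 2 or 5 years, which may give a substantial proportion rather than a rare event. Section 10.4.1 names no link for its adjusted model, so placing risk category, age and gender in the identity-link model is an inference from section 10.4. The unadjusted model with trial group alone is saturated under working independence and yields a difference without difficulty. A rule for non-convergence is commonly left to the SAP, which is not shown.

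Most of this stands, and it limits the size of the point. Three stronger readings should be set aside:

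- *The identity-link model will fail here.* No expected proportion is given, and without a risk-category effect there were no failures from 20% upwards in the main run.
- *It fails just as often with practice-level covariates.* On aggregate rows it did so only under strong effects. With 150 patients per practice, between-practice SD 0.6 and out-of-range fits counted, a log odds ratio of 0.4 per SD of SEIFA (other factors scaled to it) gave 69% failure at 1% and 24% at 10%. At 0.2 the rates were about 10% at 1% and 0% from 10% up. Nothing in the protocol points to the stronger case.
- *The missing fallback is itself an error.* It is not; the point concerns models that the protocol does name.

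The reply does not reach the mislabelled odds ratio or the p value from an unlisted model. Nor does it remove the possible sparseness of risk categories, which section 10.4.1 makes central by testing an interaction with them.

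**Conclusion.** The point holds in two parts. The wording error is certain: the count regression does not give an odds ratio, and the p value is assigned to a model that the plan does not list.

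The fragility of the identity-link model is conditional. It matters if the section 10.4.1 covariates enter that model and either the proportion is low or a rare risk category has a much lower proportion than the rest. Under the assumptions above, failure ranged from about 0% (20% to 55%, no risk effect), through 25% to 43% (at 5%, no risk effect), to over 90% (at 5% to 10%, odds ratio 0.3 in rare categories). These rates also depend on software and on the definition of failure. If the aggregate reports carry no patient breakdown and practice-level effects are modest, there is little problem.

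A reader might infer that a standardised logistic model gives the same quantity without fail. That goes too far. The standardised difference is a marginal effect and equals the identity-link coefficient exactly only under additivity. Sparse categories can trouble the logistic model too: it failed in up to 43% of datasets in the sparsest cell. With a 1% risk category among 6,000 patients (100 × 60), a 2% base and odds ratio 0.3, the proportion is 0.006 / 0.986 = 0.0061, so 60 × 0.0061 = about 0.4 events are expected. The supported claim is that it converges far more often. This is a worthwhile, low-cost correction, not a flaw that invalidates the analysis.

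**What to change.** For the outcomes expressed as proportions, replace the modelling sentence in section 10.4 with wording such as: *A logistic GEE clustered by general practice, with robust standard errors and the pre-specified covariates, will supply the odds ratio and the p value. The marginal risk difference and risk ratio will be obtained from the same model by standardisation over the trial population, with 95% confidence intervals by the delta method or a practice-level bootstrap.* State that the adjusted model in section 10.4.1 is this model.

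If a Poisson or negative binomial model is kept for numbers of tests or recommendations, call its estimate a rate ratio and take its p value from that model.

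The cost is a paragraph of protocol or SAP text and a few lines of code, with no change to data collection. The price in interpretation is that the absolute effect becomes a marginal one and should be labelled so. Sparse risk categories will still need care.

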10.2. Trial design

Following recruitment and informed consent, baseline data audits and practice surveys will be undertaken. After baseline data collection, practices will be allocated to the intervention and control arms. After an initial 6 months of usual care in all sites, the intervention will be delivered, and a mid-trial implementation survey undertaken with the intervention sites. At 12 months, the post-trial audit will be undertaken and post-trial surveys to measure the implementation effectiveness and secondary outcomes.

The 6-month period between recruitment and intervention delivery is being used as a **wash out period**. At recruitment, all practices may be exposed or most susceptible to incidental messaging relating to the NBCSP. The wash out period will ensure that we are best able to study the effects of the intervention. During this 6-month period, we will provide briefing and support to the intervention practices via the CTCs.

The flowchart of study procedures is provided in Figure 1 with the trial timeline outlined in the schedule of events ([see 10.8](#)). The dates displayed in the Figure 1 timeline are indicative and dependent on HREC approval. No activities will commence without HREC approval.

Figure 1. Trial Flowchart

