10.5. Allocation and blinding process

Randomisation for this study will be carried out at the level of general practice. Each practice will be allocated to the intervention or usual care arm using a random computer-generated sequence by the Daffodil Centre research team. To account for differences in region-specific NBCSP screening rates, the randomisation will be stratified by participating states (NSW and WA). In each state, the same number of practices will be allocated to the intervention and usual care arms. Accordingly, GPs, general practice staff and their patients will be assigned to the intervention or usual care arm based on the assignment of their general practice.

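### Sections 10.4, 10.4.1 and 10.5 disagree on the stratification factors, and the clinical co-primary models omit both state and the baseline audit value, which costs precision

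*Protocol*

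**What the plan says.** **General rule (Protocol, Section 10.4).** The rule covers all outcomes: "Both the primary and secondary outcomes will be compared between the intervention and control groups using poisson or negative binomial regression". On covariates, it states that these models "will adjust for the randomisation stratification factors (e.g., practice size, state, rurality, socioeconomic indexes for areas (SEIFA". Correlation within practices is handled separately, through "generalised estimating equations with robust standard errors to allow for clustering by general practice". The covariate rule therefore applies to completed tests, and it names state.

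**Randomisation (Protocol, Section 10.5).** Here "the randomisation will be stratified by participating states (NSW and WA". The reason given is "To account for differences in region-specific NBCSP screening rates". Arms are to be of equal size within each state. No other stratification factor appears in this section.

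**Models for the clinical co-primary (Protocol, Section 10.4.1).** Three are listed:
- one with arm alone: "The first model (unadjusted model) will use the trial group as the sole fixed predictor";
- one that extends it with patient and practice characteristics: "The second model (adjusted model) will add guideline risk category, gender, age, and socioeconomic status of the practice";
- a final model that examines the interaction of arm with risk category.

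State is in none of them.

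**Baseline data (Protocol, Section 10.2).** "Following recruitment and informed consent, baseline data audits and practice surveys will be undertaken", and allocation comes afterwards. The schedule in Section 10.8 lists a baseline clinical audit and labels it as primary-outcome data. No model in Section 10.4 or 10.4.1 uses a baseline value.

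**The concern.** An analyst fitting the completed-tests model has two incompatible instructions. Section 10.4 requires adjustment for state and for three other factors that Section 10.5 does not use, through a list left open by its 'e.g.'. Section 10.4.1 starts from arm alone and never adds state.

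Two consequences follow for precision.

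- **State.** Stratified allocation balances the arms on state, so differences between states do not contribute to the sampling variation of the arm comparison. A model without state still counts them as residual variation, and the standard error comes out too large. A robust standard error clustered on practice does not correct this.
- **Baseline.** A practice's earlier screening level is likely to predict its later level. With at most 50 practices per arm (Section 10.1.2), leaving it out forgoes precision that the planned audit could supply.

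A third issue concerns the second and third models, which condition on risk category. Section 10.4.1 ties risk to clinician judgement, and the intervention supplies decision aids (Table 1) that may influence that judgement.

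**Working it through.** **1. The sections side by side**

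| Item | 10.4 | 10.5 | 10.4.1 (completed tests) |
|---|---|---|---|
| State | adjusted for, called a stratification factor | stratification factor | absent |
| Practice size, rurality | called stratification factors | not mentioned | absent |
| SEIFA | called a stratification factor | not mentioned | second model onward |
| Baseline audit value | absent | not applicable | absent |

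**2. The plan's own figure.** There is none to reproduce. Section 10.1.2 takes up to 50 practices per arm from a rule of thumb for pilot trials. The protocol gives no standard error, intracluster correlation, state difference or baseline correlation. Nothing below overturns a stated number, and the sizes rest on assumed ranges.

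**3. Omitting state.** Let R² be the share of between-practice variance due to state (assumed). The arm-only standard error is too large by the factor 1/√(1 − R²). For R² = 0.10 this is 1/√0.90 = 1.054. As a check, a practice-level simulation used 2 states with 25 + 25 practices each (the synopsis figures; Section 7 gives 50 + 50 per state, which does not fit a total of 100). It used stratified 1:1 allocation, no true effect, robust standard errors and 4,000 runs per setting.

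| R² (assumed) | SE factor, arm only | Type I error, arm only | Type I error, arm + state |
|---|---|---|---|
| 0 | 1.00 | 5.3% | 5.3% |
| 0.02 | 1.01 | 4.9% | 5.1% |
| 0.05 | 1.03 | 4.6% | 5.0% |
| 0.10 | 1.05 | 3.7% | 4.9% |
| 0.20 | 1.12 | 2.7% | 4.8% |
| 0.30 | 1.20 | 1.9% | 5.2% |

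For scale, suppose the states differ by 5 points and practice rates have a within-state SD of 8 points (both assumed). Then √((2.5² + 8²)/8²) = √(70.25/64) = 1.048, about 5% too large.

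**4. Omitting the baseline value.** Let r be the within-arm correlation of a practice's baseline and follow-up values (assumed). Adjustment multiplies the interval width by √(1 − r²). Power is shown for 50 practices per arm, two-sided 5%, and a standardised practice-level difference of 0.5. That difference is illustrative, chosen from within the range quoted in Section 10.1.2.

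| r (assumed) | Width relative to unadjusted | Power (unadjusted 0.705) |
|---|---|---|
| 0.3 | √0.91 = 0.95 | 0.746 |
| 0.5 | √0.75 = 0.87 | 0.823 |
| 0.7 | √0.51 = 0.71 | 0.938 |
| 0.8 | √0.36 = 0.60 | 0.986 |

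**5. Extra covariates.** Adding three uninformative practice covariates to arm + state kept type I error at 4.7–5.4%. The mean standard error stayed within about 2% of the true spread of the estimates. The cost was about 1–2% in standard error.

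The simulation treats the practice result as continuous. The protocol's count and binomial models would differ in detail, but the direction rests on the same argument.

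**6. Data routes.** Completed tests come as de-identified aggregate reports (Sections 10.3.1 and 11.1.2). A practice-level baseline value fits that format. Linking a patient's baseline risk category to that patient's later result is not described. Recommendations are captured by an electronic prompt still to be developed (Section 10.3.1), so a count before allocation is not assured.

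**The case against.** **State is not missing from the plan.** Section 10.4 covers this outcome and names state. This stands: the fault is a contradiction between sections, not an absence.

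**Section 10.5 does not say that state is the only factor.** Section 10.4 may describe the intended scheme. This also stands, so the request is to reconcile the sections and adjust for whatever is actually used. Declaring state the sole stratifier could remove true stratifiers from the primary model.

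**A reader might infer that adjusting for practice size, rurality and SEIFA makes the error bars wrong.** It does not. Prespecified adjustment for such factors is legitimate, as step 5 shows. The faults are the label and the open list.

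**A reader might infer an inflated false-positive rate.** The calculations show the reverse for state, and valid but wider intervals for baseline.

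**Three models might suggest that the result can be picked afterwards.** The third asks a different question, effect modification, and a statistical analysis plan could name the primary model. This weakens the point only in part. The protocol has already fixed models that conflict with its own general rule, and the conflict has to be settled whatever another document says.

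**Risk category may not be changed by treatment.** Table 4 defines it by family history, and the record-system strategy in Table 2 mentions screening behaviours and recommendations, not risk. Bias is therefore possible but not established. That supports giving those models a supportive role and goes no further.

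**Conclusion.** The point holds as an inconsistency with a cost in precision. Section 10.4 lists factors as randomisation strata that Section 10.5 does not use. Section 10.4.1 contradicts Section 10.4 by omitting state from the clinical co-primary models, and no model uses the baseline audit.

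If state is prognostic, as Section 10.5 presumes, the arm-only standard error is conservative: about 1–5% too large if state explains 2–10% of between-practice variance. The baseline value is the larger matter. Adjustment would bring the interval width to about 0.95–0.60 of its unadjusted value for a correlation of 0.3–0.8. At the lower end the gain is only 5%. Both ranges are assumptions, because the protocol offers no figure for either. The textual contradiction does not depend on them.

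**What to change.** 1. Reconcile Sections 10.4, 10.4.1 and 10.5 so that they give one closed list of the factors actually used in randomisation.
2. Name one primary model for completed tests: arm, the actual stratification factor or factors (state, as Section 10.5 stands), and the practice's value from the pre-allocation clinical audit.
3. For recommendations, use arm plus the same stratification factors. Add a baseline value only if the prompt records one before allocation.
4. List any of practice size, rurality and SEIFA not used in randomisation as prespecified prognostic covariates, without calling them stratification factors.
5. Describe the models that condition on risk category, including the interaction model, as supportive.

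The cost is protocol wording and slightly more analysis work. The practice-level baseline for completed tests comes from an audit already planned, so no new data collection is needed for that outcome.
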